### 6.5.2 Cycle delay

The treatment window is  $\pm 3$  days for each of the Q3W administrations. A cycle is deemed to have been delayed if the treatment is administered  $\geq 4$  days beyond the theoretical day of Q3W IMP administration. The participant may receive the next dose after recovery from the toxicity as described in Section 6.5.3. After cycle delayed, such participants may be considered for treatment resumption once the toxicity resolves or improves to Grade 1 or baseline.

Participants may have cycle delay, if toxicity occurs and the participant does not recover according to following rules:

- For Q3W IMP administration: If toxicity occurs and the participant does not recover on the day of planned administration, the cycle will be delayed; restart of study IMPs could occur only on the initiation of the subsequent cycle.
- In case of cycle delay for the recovery of toxicity, the following rules should be followed for restart or discontinuation of the treatment:
  - In case of a cycle delay up to 14 days, it is per Investigator's decision to restart the study treatment.
  - After a cycle delay of  $>14$  days and  $\leq 84$  days, it is per Investigator's decision to restart the study treatment, if a clear benefit from treatment is observed and after consultation with the Sponsor.
  - The study treatment must be permanently discontinued if the cycle delay is longer than 84 days.
- Cycle may be delayed for situations other than TEAEs such as medical/surgical events or logistical reasons not related to study therapy. Participants should be placed back on study therapy within 21 days of the scheduled delay, unless otherwise discussed with the Sponsor (for example for national or regional emergencies). The reason for this delay should be documented in the participant's study record.

### 6.5.3 General guidelines for the management of treatment-related adverse events

Participants who experience Grade  $\geq 3$  TRAEs at any time of the study (including clinically significant Grade 3 laboratory abnormalities as defined in Section 10.3.1 of the master protocol) will be required to temporarily cycle delay the IMP, unless specified otherwise in the protocol, and with the exception of the TRAEs resolving within 5 days. After cycle delay, such participants may be considered for treatment resumption once the TRAE resolves or improves to Grade 1 or baseline. Treatment resumption is at the discretion of the Investigator and Sponsor, if thought to be in the best interest of the participant, except when specified otherwise in this protocol, or if the event has required the IMP temporary interruption for more than 84 days from the last scheduled dose.

The cycle delay of treatment for Grade 2 events is left at the discretion of the Investigator unless otherwise specified in this protocol.

No cycle delay of treatment or dose modification is required for Grade 1 events.

Dose reduction for SAR444245 from  $\blacksquare \mu\text{g}/\text{kg}$  to  $\blacksquare \mu\text{g}/\text{kg}$  or another lower dose may be decided when specified in the protocol or following discussions with the Sponsor.

The final decision on dose modification and/or corrective therapy will be based on the Investigator's judgment, in the best interest of the participant.

Recommended guidelines for the management of specific AEs including irAE, CRS, Vascular Leak Syndrome (VLS) and IRRs are presented in [Section 6.5.4](#).

### 6.5.4 Guidelines for the management of specific adverse events

Specific adverse events described in sections below may classify as adverse events of special interest (AESIs), depending on grading according to National Cancer Institute- Common Terminology Criteria for Adverse Event (NCI-CTCAE) V5.0 (see Section 8.3.8 of the master protocol). In case a specific adverse event meets the AESI definition it must be documented in the e-CRF.

#### 6.5.4.1 Infusion-related reactions (IRR)

Participants should routinely receive premedication as detailed in Section 6.1.2.1 of the master protocol prior to SAR444245 administration, to prevent or reduce the incidence or severity of IRRs.

An IRR in this study is defined as any signs or symptoms which develop during the infusion or up to 24 hours after the completion of the infusion. The term IRR indicates only a specific temporal relationship with the infusion and does not specify a particular mechanism underlying the signs or symptoms.

Pembrolizumab may cause severe or life-threatening infusion-reactions including severe hypersensitivity or anaphylaxis. Signs and symptoms usually develop during or shortly after drug

infusion and generally resolve completely within 24 hours of completion of infusion. Dose modification and toxicity management guidelines on pembrolizumab-associated infusion reaction are provided in [Table 2](#).

After an IRR due to pembrolizumab infusion (Grade 3 or Grade 4), the SAR444245 infusion will be delayed and can be administered after resolution of symptoms. The Investigator should discuss with the Sponsor’s Medical Monitor if the SAR444245 infusion needs to be delayed more than 1 day.

Guidelines for the management of SAR444245 IRR events are provided in [Table 3](#). Participants who develop Grade 2 IRR should have the next SAR444245 infusion given at half the infusion rate. For instructions on premedication at subsequent dosing, please see Section 6.1.2.1 of the master protocol.

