## **8.2 SAFETY ASSESSMENTS**

The main anticipated adverse effect for the combination of SAR444245 with other anticancer therapies includes manifestations of cytokine release that can range from fever to hypoxia to hypotension, with or without manifestations that may include any of the organ systems. These mild events occur between around 12 to 18 hours after the first administration and a more intensive monitoring of vital signs is planned during that period. Targeted physical exams and standard laboratory tests will be conducted to monitor potential changes in the main body functions. Measurement of cytokines in plasma are planned at relevant timepoints. White blood cell differential count will be measured to monitor for transient lymphopenia which is commonly observed in the first few days following SAR444245 infusion. Eosinophilia that is surrogate to VLS will also be monitored. IL-5, which is also a marker of VLS, will be included in the PDy cytokine panel. Combining SAR444245 with other anticancer therapies may increase the frequency and severity of immune-related adverse events related to other anticancer therapies. Immune-mediated endocrinopathies involving the thyroid being the most frequent, T3, T4, TSH, and cortisol level will be monitored. When clinically indicated, on-treatment ECG, LVEF and troponin will be assessed and compared to baseline. More details on the safety assessment are provided below. Planned time points for all safety assessments are provided in the SoA.

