##### ***SAR444245***

- **Formulation:** SAR444245 is provided as a 2 mg/mL concentrate for solution for infusion in a single-dose vial with an extractable volume of 1 mL.
- **Route of administration:** intravenous (IV) infusion.
- **Dose regimen:** 24 µg/kg administered as an IV infusion over 30 mins every 3 weeks on Day 1 of each cycle (21 days per cycle) for **up to 35 cycles.**

Study sites should make every effort to target infusion timing to be as close to 30 minutes as possible. However, given the variability of infusion pumps from site to site, a window of -5 minutes and +10 minutes is permitted.

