**Table 3 - SAR444245 Infusion-related reaction dose modification and treatment guidelines**

| NCI CTCAE Grade   | Treatment   |
|---|---|
| Grade 1
Mild transient reaction; infusion interruption not indicated; intervention not indicated  | If IRR happens during infusion, continuation of SAR444245 a infusion is per Investigator's judgment following close direct monitoring of the participant's clinical status.
SAR444245 infusion may be interrupted at any time if deemed necessary.
If interrupted, IRR will be classified as Grade 2 as per NCI-CTCAE definition.
If IRR happens after completion of infusion, increase monitoring of vital signs as medically indicated until the participant is deemed medically stable in the opinion of the investigator.   |
| Grade 2
Therapy or infusion interruption indicated but responds promptly to symptomatic treatment (eg, antihistamines, NSAIDs, narcotics, IV fluids); prophylactic medications indicated for ≤24 hrs. | Interrupt SAR444245 infusion.
If symptoms resolve within 1 hour of interrupting drug infusion, the infusion may be restarted at 50% of the original infusion rate. Otherwise dosing will be held until symptoms resolve and the participant will be premedicated for the next scheduled dose according to Section 6.1.2.1 of the master protocol.
Give the next infusion at half the infusion rate.
During or after completion of infusion, additional appropriate medical therapy may include but not limited to IV fluids, antihistamines, NSAIDs, acetaminophen, narcotics.
Increase monitoring of vital signs will be as medically indicated until the participant recovers. |

| NCI CTCAE Grade   | Treatment  |
|---|--|
| 
Grade 3
Prolonged (ie, not rapidly responsive to symptomatic medication and/or brief interruption of infusion); recurrence of symptoms following initial improvement; hospitalization indicated for other clinical sequelae
 | 
Permanently discontinue SAR444245. The participant can continue treatment with the other anti-cancer therapy in combination
During or after completion of infusion, additional appropriate medical therapy may include but is not limited to epinephrineb, IV fluids, antihistamines, NSAIDs, acetaminophen, narcotics, oxygen, vasopressors, corticosteroids.
Increase monitoring of vital signs as medically indicated until the participant recovers.
  |

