**Table 4 - Guidelines for the management of suspected cytokine release syndrome (CRS)**

| Event severity (ASTCT CRS Consensus Grading)  | Recommended SAR444245 dose modification and supportive care guidelines   |
|---|--|
| 
Grade 1
 
 
• Fever (Temperature <math>\geq 38^{\circ}\text{C}</math>)b
 
• No hypotension
 
• No hypoxia
 
   | 
No dose modification of SAR444245a
 
Appropriate symptomatic treatment may include but is not limited to IV fluids (care should be taken to not excessively hydrate if evidence of vascular leak), antihistamines, NSAIDs and acetaminophen.
 
Close direct monitoring of the participant's clinical status. Clinical and laboratory monitoring should initially be performed daily, then less frequently as the participant improves.
  |
| 
Grade 2
 
 
• Feverb (Temperature <math>\geq 38^{\circ}\text{C}</math>)
 
• Hypotension not requiring vasopressors
 
• and/orc hypoxia requiring low-flow nasal cannulad or blow-by.
 
  | 
Temporarily interrupt SAR444245 if event occurs during infusion
 
Additional appropriate medical therapy may include but is not limited to IV fluids (care should be taken to not excessively hydrate if evidence of vascular leak), antihistamines, NSAIDs and acetaminophen.
 
Increase monitoring of vital signs, cardiac and other organ functions closely as medically indicated until the participant recovers. Transfer to ICU may be required.
 
For participants with comorbidities, older age, or with oxygen requirement, hypotension, or participants in whom symptoms (eg, high grade fever) that do not respond to antipyretics within 72 hours treatment with corticosteroids and/or tocilizumab or alternative therapies per site practice in CRS management should be considered, as per guidance for Grade 3 events.
 
IMP may be resumed when clinical symptoms have resolved or improved to Grade 1 and corticosteroid taper. No dose modification is required but decreasing to half the infusion rate can be considered.
 |

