| 
Grade 3
 
 
• Feverb (Temperature <math>\geq 38^{\circ}\text{C}</math>)
 
• Hypotension requiring a vasopressor with or without vasopressin
 
• And/orc hypoxia requiring high-flow nasal cannulad, face mask, nonrebreather mask, or Venturi mask
 
  | 
If CRS grade 3, temporarily cycle delay SAR444245, and resume subsequent treatment only when symptoms have resolved or improved to Grade 1.
 
SAR444245 can be either restarted at ■ <math>\mu\text{g}/\text{kg}</math> or permanently discontinued, as clinically indicated.
  |
| 
Grade 4
 
Life-threatening consequences; urgent intervention indicated
 
 
• Feverb (Temperature <math>\geq 38^{\circ}\text{C}</math>)
 
• Hypotension requiring multiple vasopressors (excluding vasopressin)
 
• And/orc hypoxia requiring positive pressure (eg, CPAP, BiPAP, intubation and mechanical ventilation)
 
 | 
If CRS Grade 4, permanently discontinue SAR444245.
 
If CRS Grade 3 or Grade 4, initiate IV corticosteroids (outside of the context of CAR-T cells, corticosteroids alone maybe initiated in first intention) and tocilizumab or alternative therapies per site practice in CRS management considered, and/or epinephrine and/or other vasopressors should be administered as needed. Participants with severe CRS may require management in intensive care setting, with monitoring of clinical status and laboratory tests performed at least daily.
 
As the participant improves, the intensity of the monitoring and setting can be decreased, but the participant should not be discharged from the hospital until clinically stable. Corticosteroids can then be administered IV or orally every 8 hours for up to 3 days, then tapered over 4 days. In
   |

| Event severity (ASTCT CRS Consensus Grading) | Recommended SAR444245 dose modification and supportive care guidelines  |
|--|---|
|  | 
general, tapering of steroids can start when vasopressors and high-flow oxygen are no longer needed.
 
CRS is considered resolved when there is sustained resolution of fever and there is no longer a need for oxygen supplementation to relieve hypoxia nor vasopressors to maintain blood pressure; however, normalization of temperature alone does not define resolution of CRS.
   |

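### Substudy 01 defines infusion-related reaction by timing alone, so one event can be both IRR and CRS, and the two dosing tables conflict when the two scales grade it differently

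*Protocol*

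**What the plan says.** Substudy 01 section 6.5.4.1 defines an IRR as "any signs or symptoms which develop during the infusion or up to 24 hours after the completion of the infusion" and adds: "The term IRR indicates only a specific temporal relationship with the infusion and does not specify a particular mechanism underlying the signs or symptoms". SAR444245 IRRs are graded by NCI-CTCAE and managed under Table 3, where Grade 3 reads: "Permanently discontinue SAR444245. The participant can continue treatment with the other anti-cancer therapy in combination".

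Section 6.5.4.3 of the same document has CRS graded by ASTCT criteria, integrated with central cytokine results, and managed under Table 4. For Grade 2, once symptoms have settled: "No dose modification is required but decreasing to half the infusion rate can be considered". For Grade 3: "If CRS grade 3, temporarily cycle delay SAR444245, and resume subsequent treatment only when symptoms have resolved or improved to Grade 1". The next sentence allows either a restart at a dose that is blacked out or permanent discontinuation.

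Master protocol section 8.2 describes cytokine-release manifestations as the main anticipated adverse effect and says: "These mild events occur between around 12 to 18 hours after the first administration". Master section 8.3.8 lists IRR Grade 2 or higher and CRS Grade 2 or higher as separate adverse events of special interest (AESIs). Master section 9.4.3.5 summarises AESIs and presents CRS separately on the ASTCT scale.

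**The concern.** A definition by timing alone takes in anything that starts within a day of dosing, and the early cytokine reactions expected with this drug start within a day. Neither section 6.5.4.1 nor section 6.5.4.3 takes CRS out of IRR or ranks Table 3 against Table 4. Substudy 01 section 2.3.1.1 even lists CRS among the infusion-related reactions of pembrolizumab. The protocol draws this kind of line elsewhere: section 6.5.4.5 says that ICANS is outside the definition of CRS.

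Two things are at stake. First, IRR and CRS rates by grade are key safety outputs for an IL-2 combination. If sites may record the same event as IRR, as CRS or as both, neither rate compares cleanly across sites or cohorts. Second, the label can steer whether SAR444245 continues, and so exposure to the combination whose response rate is the primary endpoint. The IRR label also drives the rules for omitting or restarting premedication in master section 6.1.2.1.

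**Working it through.** The documents state no figure on this point, so there is none to reproduce. The check has four parts.

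**1. Does the IRR window contain the cytokine-release period?** Inputs: the infusion is "administered as an IV infusion over 30 mins every 3 weeks on Day 1 of each cycle"; "a window of -5 minutes and +10 minutes is permitted", which gives 25 to 40 minutes; the IRR window runs to 24 h after completion; the cytokine-release period is about 12 to 18 h after the first administration. The window opens at 0 h. Its end, counted from the start of infusion, is infusion length + 24 h:

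- 25 min: 25/60 + 24 = 24.42 h, which is 6.42 h beyond 18 h
- 30 min: 30/60 + 24 = 24.50 h, 6.50 h beyond
- 40 min: 40/60 + 24 = 24.67 h, 6.67 h beyond
- 60 min (30 min at half rate): 60/60 + 24 = 25.00 h, 7.00 h beyond

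The 12 to 18 h period lies wholly inside in every case. It also does so if counted from the end of infusion, since 18 is less than 24.

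**2. Same grade number on both scales.**

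| Grade | Table 3 (IRR) | Table 4 (CRS) | Comparison |
|---|---|---|---|
| 1 | No dose change mandated | No dose modification | Agree |
| 2 | Half rate directed for next infusion | No modification required; half rate optional | Differ in force |
| 3 | Permanent discontinuation of SAR444245 | Cycle delay, then restart or discontinuation | Conflict on restart |
| 4 | Permanent discontinuation | Permanent discontinuation | Agree |

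**3. Different grade numbers for one event.** The scales measure different things. Table 3 Grade 3 turns on slow response to treatment, symptoms that return after first improving, or admission for other sequelae. ASTCT grade turns on vasopressor and oxygen needs. Take fever of 39 °C with hypotension 14 h after dosing, corrected with fluids, then returning, with no vasopressor at any time. The return makes it IRR Grade 3, for which Table 3 directs permanent discontinuation. Without a vasopressor or high-flow oxygen it is CRS Grade 2, for which Table 4 requires no dose modification. Fever alone that is slow to settle is IRR Grade 3 and CRS Grade 1. This is not a forced case: the Grade 2 row of Table 4 itself provides for symptoms still unresponsive to antipyretics at 72 hours and then allows resumption without dose modification.

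**4. Size.** Master section 4.3 reports 13 first-in-human patients with any-grade CRS. The group sizes there are 38 monotherapy, 20 with pembrolizumab and 5 + 5 = 10 with cetuximab, and 38 + 20 + 10 = 68. So 13/68 = 19.1%, and 0.191 × 40 = 7.6, or about 8 in a cohort of 40. This would be the number open to relabelling only if the rate carried over and every case began within 24 h of infusion.

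**The case against.** Several texts soften the problem.

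- Master section 10.3.3 asks for a diagnosis rather than its signs and symptoms wherever possible, so a recognised CRS would naturally be recorded as CRS. That is a fair reading, but it does not take the event out of the IRR definition or say which table governs.
- Substudy 01 section 6.5.1 resolves conflicting recommendations by the most conservative one. It is worded for a participant with several toxicities, not one event with two names. Stretched to fit, it would settle dosing, but it would leave Table 4's Grade 3 restart option without effect for any event that also meets IRR Grade 3. It does nothing about counting.
- Substudy 01 section 6.5.3 calls the guidance recommended and leaves the final dosing decision to the investigator. So the label does not by itself compel a stop. Judgment exercised site by site also does not make labels uniform.
- The ASTCT notes count fever, hypotension and hypoxia only when no other cause explains them. IRR names no cause, so this does not separate the two terms.
- CRF completion guidance sits in a document not shown (master section 10.1.7) and may contain a recording rule. The two dosing tables are nonetheless in the protocol.

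A reader might infer three stronger things that the documents do not support. First, that every CRS is also an IRR: section 8.2 speaks of mild events at an approximate time after the first dose and does not bound all CRS. Second, that the dosing instructions are generally opposite: Grades 1 and 4 agree, Grade 2 differs only in force, and Grade 3 CRS also permits discontinuation. Third, that reported rates will move by 19 points: the 13 cases were graded by CTCAE, pool several doses, schedules and regimens, come partly from before prophylactic hydration was mandated, and have no onset times and no full grade breakdown, while the AESI overlap concerns only Grade 2 or higher.

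**Conclusion.** The point holds in a limited form. An event starting within 24 h of infusion can meet both definitions, and no text in section 6.5.4.1 or 6.5.4.3 says how to classify it or which table applies. Followed as written, the tables give incompatible instructions in two situations: a prolonged or recurrent event that is IRR Grade 3 but CRS Grade 1 or 2, and an event that is Grade 3 on both scales, where only Table 4 allows a restart. The same gap permits double or inconsistent counting of two separate AESIs.

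The frequency is unknown. About 19%, or 8 per 40, is an upper bound that assumes the pooled first-in-human rate transfers, that all onsets fall within 24 h, and that every such event is labelled differently. No effect on the response rate can be computed: participants who stop SAR444245 stay in the efficacy population (master Table 6), so only exposure would change. The finding is made on the Substudy 01 text; the matching sections of the other substudies were not available to check.

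**What to change.** The sponsor should reconcile Substudy 01 sections 6.5.1, 6.5.4.1 (with Table 3) and 6.5.4.3 (with Table 4). Section 6.5.4.1 should state whether an event meeting CRS criteria is also recorded as an IRR, with one AESI term per event, and which table governs when both could apply. Which dosing consequence should prevail is a clinical decision for the sponsor, and none is proposed here. For reporting, add one category, IRR or CRS with onset within 24 h of infusion, beside the separate IRR and CRS rates, so that at least one figure does not depend on the label.

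Cost: amendment wording, matching eCRF completion guidance and one extra table. No new assessments are needed.

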## **6.5 DOSE MODIFICATION**

### **6.5.1 General rules**

Dose modifications for SAR444245 is permitted according to the guidelines described in this section. Pembrolizumab dose reductions are not permitted. Pembrolizumab treatment may be interrupted or discontinued due to toxicity.

Dose modifications different from those stated in the protocol should only be made in consultation with the Sponsor, unless required for immediate participant safety.

**Cycle delay** (ie, Day 1 should be delayed for all IMPs) is permitted in case of treatment-emergent adverse event (TEAE). Dose modification will be made according to the worst grade of toxicity observed within a cycle. If a participant experiences several toxicities and there are conflicting recommendations, the most conservative recommended dose adjustment should be followed. Once a dose has been decreased, intra-patient re-escalation back to the previous dose level is not permitted.

Administration of the study treatment will be discontinued in the event of a TEAE that persists despite appropriate dose modifications or any other TEAE that, in the opinion of the Investigator, warrants discontinuation.

If any of the IMP components is permanently discontinued, the other IMP component can be continued until disease progression or other criteria as detailed in Section 7.1.1 of the master protocol are met. In this case, it is partial permanent discontinuation, and the end of treatment (EOT) assessment will be 30 days after the date of the last administration of the remaining IMP. When all IMP components are permanently discontinued, it is full permanent discontinuation.

All changes to study treatment administration must be recorded in the electronic case report form (e-CRF).

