**Table 2 - Pembrolizumab infusion-related reaction dose modification and treatment guidelines**

| NCI CTCAE Grade   | Treatment   | Premedication at subsequent dosing   |
|---|---|--|
| Grade 1
Mild transient reaction; infusion interruption not indicated; intervention not indicated  | Increase monitoring of vital signs as medically indicated until the participant is deemed medically stable in the opinion of the investigator.  | None   |
| Grade 2
Therapy or infusion interruption indicated but responds promptly to symptomatic treatment (eg, antihistamines, NSAIDs, narcotics, IV fluids); prophylactic medications indicated for ≤24 hrs. | Stop Infusion.
Additional appropriate medical therapy may include but is not limited to: 
 
• IV fluids,
 
• Antihistamines,
 
• NSAIDs,
 
• Acetaminophen,
 
• Narcotics.
 
 Increase monitoring of vital signs as medically indicated until the participant is deemed medically stable in the opinion of the investigator.
If symptoms resolve within 1 hour of stopping drug infusion, the infusion may be restarted at 50% of the original infusion rate (eg, from 100 mL/hr. to 50 mL/hr.). Otherwise dosing will be held until symptoms resolve and the participant should be premedicated for the next scheduled dose.
Participants who develop Grade 2 toxicity despite adequate premedication should be permanently discontinued from further study drug treatment | Participant may be premedicated 1.5 h (±30 minutes) prior to infusion of pembrolizumab with:
Diphenhydramine 50 mg po (or equivalent dose of antihistamine).
Acetaminophen 500-1000 mg po (or equivalent dose of analgesic). |

| NCI CTCAE Grade  | Treatment  | Premedication at subsequent dosing |
|--|--|------------------------------------|
| Grades 3 or 4   | 
 
• Stop Infusion.
 
   | No subsequent dosing               |

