| Grade 3:
Prolonged (ie, not rapidly responsive to symptomatic medication and/or brief interruption of infusion); recurrence of symptoms following initial improvement; hospitalization indicated for other clinical sequelae (eg, renal impairment, pulmonary infiltrates) | Additional appropriate medical therapy may include but is not limited to: 
 
• Epinephrine*,
 
• IV fluids,
 
• Antihistamines,
 
• NSAIDs,
 
• Acetaminophen,
 
• Narcotics,
 
• Oxygen,
 
• Pressors,
 
• Corticosteroids.
 
  |                                    |
| Grade 4:
Life-threatening; urgent intervention indicated   | Increase monitoring of vital signs as medically indicated until the participant is deemed medically stable in the opinion of the investigator. 
 
• Hospitalization may be indicated.
 
 *In cases of anaphylaxis, epinephrine should be used immediately.
Participant is permanently discontinued from further study drug treatment. |                                    |

Appropriate resuscitation equipment should be available at the bedside and a physician readily available during the period of drug administration.

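### Substudy 01, Table 2 does not name the drug it stops after a pembrolizumab infusion reaction, while 6.5.4.1 allows SAR444245 after recovery, so sites may act differently on SAR444245.

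*Protocol*

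**What the plan says.** Four places in Substudy 01 (Cohort A1, SAR444245 plus pembrolizumab) bear on the question.

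- **Section 6.5.4.1, text.** "After an IRR due to pembrolizumab infusion (Grade 3 or Grade 4), the SAR444245 infusion will be delayed and can be administered" once symptoms have resolved. The investigator is to discuss the case with the sponsor's medical monitor "if the SAR444245 infusion needs to be delayed more than 1 day".
- **Table 2, Grades 3 or 4.** The treatment column says "Participant is permanently discontinued from further study drug treatment". The column on premedication at later doses says "No subsequent dosing". Neither entry names a drug. The table is titled "Pembrolizumab infusion-related reaction dose modification and treatment guidelines".
- **Table 2, Grade 2.** "Participants who develop Grade 2 toxicity despite adequate premedication should be permanently discontinued from further study drug treatment". Again no drug is named.
- **Section 6.5.1.** "If any of the IMP components is permanently discontinued, the other IMP component can be continued until disease progression", or until another discontinuation criterion is met. This is called partial permanent discontinuation. It becomes full when all components have stopped.

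Section 6.1.1 defines both SAR444245 and pembrolizumab as investigational product. Table 3, on reactions to SAR444245, names SAR444245 as the drug to stop at Grades 3 and 4 and adds that the participant can continue the other therapy.

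**The concern.** The text and the table it cites deal with the same event, a Grade 3 or 4 pembrolizumab infusion reaction. The text foresees giving SAR444245 after recovery, with sponsor contact called for only if the delay exceeds a day. The table discontinues the participant from an unnamed 'study drug'. A site working from the table alone could stop both drugs; a site working from the text could give SAR444245.

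At stake first is consistent handling of participants after a reaction that, at Grade 4, the table itself defines as life-threatening. Second is how the case enters the safety data. Adverse events leading to partial and to full discontinuation are tabulated separately (Master Protocol 9.4.3.5), and both the end-of-treatment visit and the on-treatment period run from the last dose.

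**Working it through.** The protocol gives no figure to reproduce here. The check is a comparison of wording, followed by short arithmetic on the consequences.

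**Step 1. Does 'study drug' have a fixed meaning?** Substudy 01 defines the investigational product (6.1.1) but not 'study drug'. Exclusion criterion E 16 of the Master Protocol uses the term generically, for the first dose on study. The term is therefore not reserved for pembrolizumab.

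**Step 2. Test each meaning against the other passages.**

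| Meaning of 'study drug' in Table 2 | Against 6.5.4.1 text | Against 6.5.1 |
|---|---|---|
| Pembrolizumab only | Agrees: SAR444245 may follow after recovery | Agrees: partial discontinuation |
| Both drugs | Conflicts: SAR444245 could not be given | Overrides the permission to continue the other component |

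**Step 3. Which meaning does the wording favour?**

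- *For both drugs:* Table 2 discontinues the participant, whereas Table 3 discontinues a named drug. Table 3 says that the partner may continue; Table 2 has no such sentence.
- *For pembrolizumab only:* the title of Table 2; the Grade 2 premedication cell, which refers to the pembrolizumab infusion; section 6.5.1; and the different words used where everything is meant to stop, namely all study drugs (6.5.4.4) and full study treatment (Table 5, footnote b).

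The second group is substantial, but a site has to assemble it from several places.

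**Step 4. The Grade 2 row.** The sentence in 6.5.4.1 on delaying SAR444245 after a pembrolizumab reaction covers Grades 3 and 4 only. For Grade 2 despite premedication, only the general rule in 6.5.1 counters the broad reading of Table 2.

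**Step 5. Consequences for the data.**

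- *Classification:* full discontinuation on the broad reading, partial on the narrow one if SAR444245 continues.
- *Clocks:* under 6.5.1 the end-of-treatment assessment is 30 days after the last dose of the remaining component. Under Master Protocol 9.4.1 the on-treatment period ends 30 days after the last dose of investigational product. Each further 21-day cycle of SAR444245 moves both by about 21 days. For a reaction in Cycle 1 and no later delays, the maximum of 35 cycles gives (35 − 1) × 21 = 714 days.
- *Response rate:* one dose of either agent, even incomplete, puts a participant in the exposed population. Permanent discontinuation or an evaluable post-baseline tumour assessment then puts the participant in the efficacy population (Master Protocol, Table 6). The definition of the rate and its Clopper-Pearson interval do not depend on the reading.

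**Step 6. Number of cases.** No rate of Grade 3 or 4 pembrolizumab infusion reactions is given. Assuming 1% to 5% of the planned 40 participants: 40 × 0.01 = 0.4 and 40 × 0.05 = 2. Grade 2 reactions despite premedication would add to this by an unknown number.

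**The case against.** The strongest reply is that the passages, read together, yield one coherent rule. Table 2 is about pembrolizumab by title. Its entry on later dosing sits in a column whose Grade 2 cell speaks of pembrolizumab infusions. The text of 6.5.4.1 says directly what happens to SAR444245, and 6.5.1 supplies the general rule. On that view the missing partner-drug sentence is a drafting asymmetry. Cases can also be classified, and the clocks set, from the doses actually given.

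Most of this stands. It shows that a consistent reading exists, and it rules out calling the passages irreconcilable. It does not remove the defect: a toxicity table consulted during a severe reaction should itself say which drug it stops. That a case can be classified afterwards does not help if two sites have treated the same event differently.

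A reader might go further in three ways that the documents do not support.

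- *That sites will certainly diverge.* Divergence is possible, not established.
- *That the participant would be withdrawn.* Master Protocol 7.1.1 keeps a participant in the study after permanent discontinuation of treatment.
- *That a reaction within 24 hours of both infusions falls under two tables with opposite results, so that a new attribution rule is needed.* This presupposes the broad reading of Table 2. The dosing sequence in 6.1 is redacted, so the order and spacing of the infusions cannot be judged. The investigator already assesses causality (Master Protocol 10.3.3), and 6.5.1 already applies the most conservative adjustment when recommendations conflict.

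**Conclusion.** The point holds as an unresolved ambiguity. Table 2 leaves its drug unnamed in the Grade 2 (despite premedication) and Grade 3/4 entries. One available reading conflicts with 6.5.4.1 and the other agrees with it. Sites may therefore act differently on SAR444245 after a severe pembrolizumab reaction.

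The statistical effect is small: the partial or full discontinuation label and the timing of the end-of-treatment and on-treatment periods, for about 0.4 to 2 of 40 participants at the assumed rates plus any Grade 2 cases. The sample size, the response-rate definition and its interval are untouched. The correction is still worth making because the possible actions after a severe reaction are opposite and the cost is slight. The conclusion rests on the wording of Substudy 01 and the Master Protocol; no view is taken on which clinical rule is right.

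**What to change.** Reconcile 6.5.4.1, Table 2 and 6.5.1 of Substudy 01. In Table 2, in the Grade 2 row (reaction despite adequate premedication) and the Grade 3/4 row, replace 'study drug' with the drug or drugs meant, and make the Grade 3/4 entry on later dosing equally specific. State in both rows, as Table 3 does, whether the partner drug may continue. The sponsor decides which rule applies; partial or full discontinuation then follows from the definitions already in 6.5.1.

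The cost is a few words in one table and a check that the adjoining text agrees. No procedure, visit, data item or analysis is added.
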